13	Study Costs	38
14	Publication Policy	38
15	References.....	39
17	Appendix 1 – [REDACTED]	40
18	Appendix 2 – [REDACTED]	50
19	Appendix 3 – Randomization.....	51
20	Appendix 4 – [REDACTED]	52
21	Appendix 5 – [REDACTED]	65
22	Appendix 6 – [REDACTED]	65
23	[REDACTED] 7 – [REDACTED]	65
24	Appendix 8 – [REDACTED]	65
25	Appendix 9 – [REDACTED]	65

26 Appendix 10 – Adverse Event Case Report Forms	67
27 Appendix 11 – Clinical Trial Product Defect Notification Form.....	70

1 Study Objective

The objective of this Design Validation clinical investigation is to compare the visual clinical performance of the [REDACTED] investigational contact lens to [REDACTED] contact lenses. CooperVision, Inc. (CVI) is aiming to compare visual acuity and subjective vision ratings of vision quality between two CooperVision lenses: [REDACTED] versus [REDACTED] in habitual soft lens wearers. The [REDACTED] lens is a daily disposable investigational lens in this study (as this lens has not been yet approved or commercially available in the US), the [REDACTED] is commercially available in the US for myopia control.

[figure not shown]
[REDACTED] lens is a silicone hydrogel daily disposable (DD) lens with a similar design to [REDACTED] hydrogel DD lenses. CooperVision, Inc. is interested in comparing visual acuity and subjective vision ratings between these two lenses of different materials to gain insight into the differences between these lenses from this aspect.

The primary outcome variable for this study is:

- High contrast, binocular, distance visual acuity (logMAR) at 1-week visit.

The secondary outcome variable is:

- Subjective vision quality (0-100 scale) at 1-week visit

2 Study Design

This will be a prospective, multiple day, double (investigator and subject) masked, randomized, bilateral crossover study comparing a Test lens against an appropriate Control lens. Each subject will wear the Test lens or the Control lens in a bilateral fashion for 7 days (+ 3 days) followed by the alternate lens for 7 days (+ 3 days). The order of lenses will be randomized.

There will be a total of 3 visits in the study as described in Section 7.5 below.

3 Study Devices and Comparator Products

3.1 Contact Lenses

A summary description of the Test and Control lenses to be used in the clinical study are shown in Table 1. The Test lens is an investigational silicone hydrogel lens with a slight modification to an approved contact lens design [REDACTED]. The Control lens is a currently marketed contact lens.

Further details regarding the investigational lens are described in the Investigator Brochure.

Table 1: Study lenses

A large black rectangular box redacting the content of Table 1: Study lenses.

3.1.1 Intended Use

In this clinical investigation, the study lenses are intended to be used as a single use. Single use lenses will be used for a maximum of one day of lens wear recommended by the Sponsor.

3.1.2 Storage of Lenses and Lens Care Solutions

The study materials must be stored in a secured area. All lenses and lens care solutions should be stored at controlled room temperature (59-86°F).

3.2 Adjunct Products

3.2.1 Contact Lens Care Products

No contact lens care is required for this study as lenses are to be worn for a single day only. No contact lens wetting drops will be used during this study.

3.2.2 Other

No other medical devices will be used in this study.

4 Justification for the Study Design

Nonclinical testing methods are not adequate to provide the information needed to advance the development of the ██████████ Contact Lens. A biocompatibility assessment has been completed and the benefit/risk assessment (see Section 5 below) supports the use of the device in this feasibility study. A synopsis of the biocompatibility assessment and prior clinical testing can be found in the Investigator Brochure.

A crossover design has been chosen since it minimizes the impact of potential sympathetic effects between the two eyes (e.g. an uncomfortable lens in one eye may impact the subjective rating of the fellow eye). The study contact lenses do not alter the physiology and hence there is no carryover effect requiring a washout period. The order effect will be tested.

The choice of comparator product was made in order to assess the clinical performance against a currently marketed product representative of generally accepted state of the art.

5 Benefits/Risks of Study Device(s) and Study Procedures

5.1 Anticipated Clinical Benefits

There might not be direct benefits to the subjects in this study, however participation in a new study may contribute to scientific research information that may be used in the development of new contact lens products. In addition, subjects will receive an examination of the front of their eyes and may have the opportunity to try a different type of soft contact lens and/or different lens care products at no cost to them.

5.2 Anticipated Adverse Device Effects

Ocular complications that may occur during the wearing of contact lenses include discomfort, dryness, aching or itching eyes, burning, grittiness, excessive tearing, discharge, hyperemia and variable or blurred vision. More serious risks may include photophobia, iritis, corneal edema or eye infection. Although contact lens-related infections are very infrequent, the possibility does exist. The incidence of infection due to daily-wear soft lenses is 0.035%.¹ Almost always an infection will occur only in one eye. This risk is assumed by 35-million Americans who currently wear contact lenses.

Subjects will need to meet the vision requirements for driving if they are old enough and plan to drive while participating in this study.

5.3 Risks Associated with Participation in the Clinical Investigation

This is considered a non-significant risk study based on United States Food and Drug Administration (FDA) guidelines due to the daily wear nature of the study. The risks associated with the investigational contact lenses have been estimated in accordance with ISO 14971. A synopsis of pre-clinical and prior clinical testing results are included in the Investigator's Brochure. Risk controls to reduce the risk as far as possible have been implemented and any residual risks will be further mitigated through close evaluation by the investigators under this clinical protocol and communicated via informed consent.

5.4 Risks of Clinical Procedures to be Utilized in the Study

Routine, non-invasive procedures will be conducted in this study. Routine clinical procedures include auto-refraction, auto-keratometry, visual acuity, anterior ocular health assessment, and

contact lens fitting will be used. In addition, standard research procedures such as high magnification imaging of the lens fit may be made using 35 mm or digital cameras, in vivo confocal microscopy, and/or specular microscopy.

5.5 Possible Interactions with Concomitant Medical Treatments

The use of contact lenses can interact with concomitant topical, ocular and/or systemic medical treatments, therefore only healthy subjects who are not currently taking concomitant medical treatments will be included in this study assure in exclusion. Artificial tears, re-wetting drops, and lubricating agents are not considered medical treatments. Only those products approved for the use with contact lenses can be used according to their indication under this protocol.

5.6 Steps That will be Taken to Control or Mitigate the Risks

The following Information for Safety for contact lens wear during the clinical study will be reviewed with each subject:

Hands should be washed and dried prior to touching the lenses for insertion or removal. If inserting the lenses yourself, they should be checked for tears and/or whether they are inside out prior to insertion. Eye rubbing should be avoided. Contact lenses should never be worn while swimming or in any other hazardous environment. The contact lenses are not to be slept in during the study or worn overnight and are to be replaced with a new pair according to the study lens wear schedule.

5.7 Rationale for Benefit-Risk Ratio

The knowledge gained from this feasibility study may lead to important conclusions regarding the ocular response and performance of new contact lens materials and designs. The potential risks for participating in this study are minimal, therefore the benefit-risk ratio is acceptable.

6 Ethics Review / Statement of Compliance

6.1 Relevant Standards / Guidelines

[figure not shown]
This study was developed in accordance with 21 CFR Part 812 Investigational Device Exemptions and the good clinical practice (GCP) principles and ethical considerations of ISO 14155 Clinical Investigation of Medical Devices for Human Subjects and Declaration of Helsinki. The detailed

descriptions of ocular Adverse Events details and the biomicroscopy grading scales are adapted from ISO 11980 Ophthalmic Optics – Contact lenses and lens care products – Guidelines for clinical investigations.

6.2 Institutional Review Board

This study will be conducted in accordance with Institutional Review Board regulations (U.S. 21CFR Part 56.103) or applicable IEC regulations. Copies of all IRB/IEC correspondence with the investigator/Sponsor will be kept on file.

This study will adhere to a protocol and informed consent document approved by the [REDACTED] [REDACTED]. Each study subpart/implementation will be submitted to Sterling for approval prior to commencing the study.

6.3 Informed Consent

Informed consent shall be obtained in writing from the subject and the process shall be documented before any procedure specific to the clinical investigation is carried out.

6.4 Clinical Trial Registration

This study will be registered, and a description of this clinical trial will be available on <http://www.ClinicalTrials.gov>, as required by U.S. Law.

7 Design of the Clinical Investigation

[figure not shown]
7.1 Study Endpoints

The primary study endpoint:

- High contrast, binocular, distance visual acuity (logMAR) at 1-week visit.

The secondary study endpoint is:

- Subjective vision quality (0-100 scale) at 1-week visit

7.2 Clinical Site

The clinical site was selected based on the availability of representative population of subjects and Investigator's clinical research experience.

The Investigators will be required to fulfill the following criteria:

- Trained and experienced in the conduct of clinical research
- Willingness to follow the study protocol
- Trained in Good Clinical Practice (GCP) and the study protocol prior to commencing the study.

7.3 Subjects

A maximum of up to 40 subjects will be enrolled in this study, in order for a minimum of 10 subjects and a maximum of up to 30 subjects, to complete the study. Each subject will be given a unique ID

number. ID numbers will not be re-used. All subjects must meet the study inclusion and exclusion criteria listed below.

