10.2 Sample Size Calculations

The target sample size for this study is 30 participants to be randomized and to wear both contact lens types. This target was determined based on the sample size calculation below:

to demonstrate non-inferiority in high contrast binocular distance logMAR visual acuity for the Test contact lens compared with the Control contact lens, the sample size estimation is based upon a one-sided paired t-test with $\alpha = 0.025$, $\beta = 0.200$ and a non-inferiority margin of 0.050 logMAR when postulating a true difference of 0.00 logMAR with a standard deviation of 0.07 logMAR a total of 26 participants is required. The target for this study will be for 30 participants to complete the study without a significant protocol deviation.

Therefore, in this study, a maximum of 40 participants may be randomized to achieve a maximum of 30 completed.

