10.3 Statistical Analysis

Statistical analysis will be undertaken by the study biostatistician. The critical measure for statistical significance is set at alpha = 5% level with a P-value ≤ 0.05 . All subjects who have completed the study will be included in the analysis.

Lens performance will be compared per study design. Descriptive statistics (e.g., mean, standard deviation) and/ or frequency of counts for categorical data may be produced for primary and/or second interests. Paired t-test may be used to compare slit lamp biomicroscopy, contact lens fit and subjective scores between study contact lens types. Where applicable, Repeated Measures Analysis of Variance (ANOVA) or paired analysis may be used to compare the variables between study visits. Binomial tests may be used to analyze the results for the frequencies of subjective and objective preferences.

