10.4 Interim Data Analysis

Interim data analysis may be performed to take business decisions. The Sponsor may stop enrollment for this study if needed after any interim read.

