11.4 Suspension or Premature Termination of the Clinical Investigation

The study may be suspended or prematurely terminated if there is sufficient reasonable cause. Written notification, documenting the reason for study suspension or termination, will be provided by the suspending or terminating party to the Investigator, the Sponsor and the Institutional Review Board (IRB), as appropriate. If the study is prematurely terminated or suspended, the Investigator will promptly inform the IRB and will provide the reasons for the termination or suspension. In terminating the clinical investigation, CooperVision and the Principal investigator will assure that adequate consideration is given to the protection of the subject's interests.

Circumstances that may warrant termination or suspension include, but are not limited to:

- Determination of unexpected, significant, or unacceptable risk to participants
- Demonstration of efficacy that would warrant stopping
- Insufficient compliance to protocol requirements
- Data that are not sufficiently complete and/or evaluable
- Determination of futility

The blinding/masking code may be broken and communicated to the Principal Investigator only in the case of an emergency, such as an Adverse Event that requires knowledge of the identity of the investigational product in order to manage the subjects' condition.

The study may resume once concerns about safety, protocol compliance or data quality are addressed and satisfy the Sponsor and IRB/EC.

Subjects will continue to receive follow-up care until they are able to be exited from the study (in the case of study termination) or are able to resume participation in the study (in the case of temporary study suspension), whereupon they will also be followed to exit.

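### Section 7.3 permits as few as 10 completers without explanation, well short of the 26 that Section 10.2 requires and of the 18 that its stated inputs give if 0.07 is the SD of the paired difference

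*Combined protocol and SAP*

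**What the plan says.** Section 7.3 (Subjects) allows up to 40 enrolled "in order for a minimum of 10 subjects and a maximum of up to 30 subjects, to complete the study".

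Section 10.2 (Sample Size Calculations) sizes the primary comparison, binocular high contrast distance acuity, with a one-sided paired t-test: alpha 0.025, beta 0.200, non-inferiority margin 0.050 logMAR. It continues: "postulating a true difference of 0.00 logMAR with a standard deviation of 0.07 logMAR a total of 26 participants is required". It then sets the aim: "The target for this study will be for 30 participants to complete the study without a significant protocol deviation". It closes with the same upper limits as Section 7.3, "a maximum of 40 participants may be randomized to achieve a maximum of 30 completed", but does not mention the lower limit of 10.

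Three other places bear on how many subjects reach the analysis:

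- Section 10.3: "All subjects who have completed the study will be included in the analysis".
- Section 10.4: "The Sponsor may stop enrollment for this study if needed after any interim read". No minimum number is given.
- Section 11.4 lists among the grounds for termination "Demonstration of efficacy that would warrant stopping", and also futility, again without a number.

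**The concern.** Two sections give different answers to the question of how many completers the trial needs. One treats 10 as an acceptable minimum; the other says 26 are needed for the primary test to have its planned power. A trial that stopped at 10 would meet Section 7.3 and would still go to the primary analysis under Section 10.3. Nothing would require the report to say that the planned power had not been reached.

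The obvious repair, replacing 10 by 26, runs into a second difficulty. Section 10.2 does not say whether 0.07 is the SD of the within-subject difference or the SD of acuity with one lens. On the natural reading for a paired t-test, the SD of the difference, 26 is not the number that the inputs give.

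At stake is an inconclusive result for a lens that is truly no worse than Control, in a study that asks subjects aged 8 to 18 to wear both lenses.

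**Working it through.** **Inputs (Section 10.2).** Margin M = 0.050, true difference 0, one-sided alpha 0.025, target power 0.80, SD 0.07. Completers: 10 (minimum, Section 7.3), 26 (stated requirement) and 30 (target).

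**Formula.** For a paired t-test with n completers and SD of the difference s, the noncentrality is M√n / s on n − 1 degrees of freedom. Power is the probability that a noncentral t variable with that noncentrality exceeds the 97.5% point of the central t.

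**Step 1: the plan's own 26, taking s = 0.07.**

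| n | noncentrality 0.05√n/0.07 | critical t | power |
|---|---|---|---|
| 10 | 2.259 | 2.262 | 52.2% |
| 17 | 2.945 | 2.120 | 79.0% |
| 18 | 3.030 | 2.110 | 81.5% |
| 26 | 3.642 | 2.060 | 93.8% |
| 30 | 3.912 | 2.045 | 96.6% |

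The smallest n reaching 80% is 18, so the 26 is not reproduced. The normal approximation gives (0.07 × (1.960 + 0.842) / 0.05)² = 15.4, so 16, which is further away. Inflating 18 for 30% dropout gives 18 / 0.70 = 25.7, so 26, but Section 10.2 states no dropout rate.

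**Step 2: the SD at which 26 is right.** 26 is the smallest n reaching 80% when s lies between about 0.0856 and 0.0875. Over that range, power is 37.9% to 36.6% at 10 completers and 87.1% to 85.7% at 30.

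**Step 3: 0.07 as a per-lens SD.** Then s = 0.07 × √(2(1 − ρ)), where ρ is the within-subject correlation. The documents give no ρ, so these values are assumptions.

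| ρ | s | power at 10 | n required for 80% |
|---|---|---|---|
| 0 | 0.0990 | 29.8% | 33 |
| 0.25 | 0.0857 | 37.8% | 26 |
| 0.5 | 0.0700 | 52.2% | 18 |
| 0.7 | 0.0542 | 73.8% | 12 |
| 0.75 | 0.0495 | 81.1% | 10 |
| 0.8 | 0.0443 | 88.7% | 9 |

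Ten completers reach 80% only from ρ of about 0.74. The figure 26 is the required number only for ρ between about 0.22 and 0.25. The two ranges do not overlap, so no single value of ρ makes 26 required and 10 sufficient.

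**Step 4: what 10 completers could show.** With an observed SD of 0.07, the half-width of the two-sided 95% confidence interval is 2.262 × 0.07 / √10 = 0.0501 logMAR, about the whole margin. Non-inferiority would then need an observed mean difference of about zero or in favour of Test. With s = 0.07, a truly equivalent lens would miss 100 − 52.2 = about 48% of the time, against the planned 20%. The half-width is 0.0348 at 18, 0.0283 at 26 and 0.0261 at 30.

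**The case against.** The strongest reply is that the plan is for 30, not 10. Section 10.2 states that target twice, and Section 7.3 gives 10 only as the lower end of a range. Nothing says that enrolment will stop at 10, that 10 triggers the analysis, or that Sections 10.4 and 11.4 are tied to it. Harm requires the sponsor to choose to stop, and to do so near the floor. Sections 4 and 5.7 also call this a feasibility study, where a low floor is less surprising. All of this stands and limits the weight of the point. It does not explain the 10: neither section links the feasibility label to that number, Section 1 calls the trial a Design Validation investigation, and Section 10.1 states a formal non-inferiority hypothesis. Some pages and appendices are not visible, so the claim is only that no visible text explains it.

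A reader might go further in three ways that the documents do not support.

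- **That 26 for 80% power and 52% power at 10 belong to one calculation.** They need different SDs. If 26 is right, power at 10 is about 37-38%; if 52% is right, 18 are required.
- **That a small number of completers makes the test invalid.** At a fixed n the t-test keeps its one-sided 2.5% error. Unadjusted repeated looks under Section 10.4 would be a different matter, which a minimum number would not solve.
- **That no non-inferiority conclusion should be drawn below the required number.** An interval that excludes the margin is valid at a fixed n whatever the planned power. Such a rule would bar a valid result at 17 completers (79.0% power with s = 0.07), and applied to Section 11.4 it would override the efficacy stop allowed there.

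**Conclusion.** The point holds as an inconsistency in the planned numbers with a conditional consequence. The minimum of 10 has no visible justification and is well below both the stated 26 and the 18 that follows if 0.07 is the SD of the paired difference. Power at 10 is about 52% on that reading and about 37-38% if the SD is the one that makes 26 correct. Only an unstated correlation of about 0.74 or more, with 0.07 as a per-lens SD, would make 10 adequate, and then 26 would not be required.

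The target of 30 is adequate on the first two readings: 96.6%, or about 86-87%. The risk is therefore an inconclusive trial if enrolment stops near the floor. The figures assume a true difference of zero and the exact paired t-test that Section 10.2 names.

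**What to change.** 1. **Section 10.2:** state whether 0.07 is the SD of the paired difference or a per-lens SD, and in the second case give the correlation. Then correct the 26 (to 18 if it is the SD of the paired difference) or correct the inputs that produced it.
2. **Section 7.3:** replace the minimum of 10 with the corrected required number. Alternatively, keep 10, label it an operational floor and state its power (about 52% if 0.07 is the SD of the paired difference).
3. **Section 10.4:** refer to the same number, and say that if enrolment stops below it the report will state the power at the number completed.

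The cost is wording. The sponsor keeps its freedom to stop enrolment; the downside for it is that the stated figure for a finish at 10 becomes less favourable. No added recruitment is needed if the required number is 18 or 26, because 30 completers are already targeted. It would exceed 30 (up to 33 at zero correlation) only if 0.07 is a per-lens SD with a correlation below about 0.09.

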7.3.1 Inclusion criteria

A person is eligible for inclusion in the study if they have:

- Are 8 to 18 years of age (inclusive)
- Have read, signed and dated:
 - Age 18 - The Participant Informed Consent Form (participant only)
 - Age 12-17 – The Parental Permission Form (participant and parent)
 - Age 8-11 - The Parental Permission Form (parent) and Assent form (participant)
- Are willing and able to follow instructions and maintain the appointment schedule.
- Are habitual daily wearers of spherical single vision soft contact lenses to correct for distance vision in each eye, including myopia control soft contact lenses as below
- Currently wears spherical soft contact lenses or myopia control soft contact lenses.
- Have a pair of wearable back-up spectacles.
- Are willing and able to wear contact lenses for at least 10 hours a day, 6 days a week while in the study.
- Are myopic with subjective refraction: -0.75D to -7.00D spherical, with an astigmatism \leq -0.75D in each eye with maximum spherical equivalent anisometropia of 1.00D
- Are correctable to a visual acuity of +0.10 logMAR or better (in each eye) with spherocylindrical subjective refraction.
- Have clear corneas with no corneal scars or any active ocular disease.
- Can be fit with the study contact lenses with a power between -0.75 and -7.00 DS; this translates to best corrected vision sphere refraction that vertexes to a CL power between -0.75 and -7.00 (inclusive) at screening visit.
- Demonstrate an acceptable fit with the study contact lenses.
- Demonstrate that they can safely and independently insert and remove contact lenses at the screening/fitting visit.

